| | Emesis | 2 | 0 | 0 | 2 |
| | Fatigue | 3 | 0 | 0 | 3 |
| | Headache 1 Day | 4 | 5 | 0 | 9 |
| | Headache > 1 Day | 1 | 2 | 0 | 3 |
| | Numbness -- appendage | 1 | 0 | 0 | 1 |
| | Nausea | 2 | 4 | 0 | 6 |
| | Paresthesia - appendage | 3 | 0 | 0 | 3 |
| | Paresthesia - face | 4 | 1 | 0 | 5 |
| | light headedness | 7 | 1 | 0 | 8 |
| | Twitch | 1 | 0 | 0 | 1 |
| | Warm Sensation | 4 | 0 | 0 | 4 |
| | Edema | 1 | 0 | 0 | 1 |
| | Ataxia | | 1 | 0 | 1 |
| Non-Significant Subtotal | | 45 | 14 | 0 | 59 |
| Significant Treatment Anticipated Events | Balance | 2 | 2 | 0 | 4 |
| | Fatigue | 1 | 0 | 0 | 1 |
| | Infection – pin site | 1 | 0 | 0 | 1 |
| | Numbness – pin site | 1 | 0 | 0 | 1 |
| | Parasthesia - appendage | 1 | 1 | 0 | 2 |
| | Parasthesia - face | 4 | 1 | 0 | 5 |
| | Parasthesia - scalp | 4 | 0 | 0 | 4 |
| | Hypesthesia - scalp | 1 | 0 | 0 | 1 |
| | Burn – pin site | 1 | 1 | 0 | 2 |
| | Significant Subtotal | 16 | 5 | 0 | 21 |

Table 2 Overall Adverse Events and Severity: ET-001

| | Event | Mild | Moderate | Severe | Total # of Events |
|-------------------|----------------------------|-----------|-----------|----------|-------------------|
| Incidental Events | Sinusitus | 0 | 1 | 0 | 1 |
| | Bronchitus | 1 | 0 | 0 | 1 |
| | Incidental Subtotal | 1 | 1 | 0 | 2 |
| | Total | 62 | 20 | 0 | 82 |

The most significant results shown in Table 2 are that all these events are indeed anticipated events and were already identified as potential events in the study protocol. Furthermore, NONE of the adverse events reported to date were severe in nature. In fact, 76 % (62/82) were Mild events, and the remainder 24% (20/82) were Moderate. Most of these events resolved either the same day (49% of the total events) or within 2 weeks of treatment (26% of the total events). Hence, 61 events (i.e. 74%) resolved within 2 weeks of the procedure.

Of all the events that did not resolve within the first 2 weeks post procedure, 14 out of 82 events (17%) resolved in more than 2 weeks (not counting the incidental sinusitis (n=1)), and 7 events (9%) were reported as ongoing.

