2.1 Primary Endpoints

2.1.1 Safety

Safety of ExAblate will be determined by an evaluation of the incidence and severity of device / treatment related complications from the first treatment day visit through ALL study follow ups. Adverse events (type, frequency, severity) are expected to be similar to those of previous studies using ExAblate TcMRgFUS for Thalamotomy

All AEs will be reported and categorized by investigators as definitely, probably, possibly, or unrelated to the device or procedure and categorized by treatment group / treatment arm.

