5.4 Statistical Considerations and Sample Size

The study will include a total of a minimum of 72 and a maximum of 80 randomized subjects in a 3:1 (treated:sham control) ratio at up to 8 sites. This sample size provides a 20% increase due to potential subject dropout from the below rationale for 60 evaluable subjects.

- The rational for this sample size is based upon the observation from the pilot study of a sample size of 15 of a 78% drop in Total CRST from a mean of 20.4 to 4.7 while the untreated sample dropped 4%. Based upon these data, the power to detect a change in the treated vs sham control is greater than 99% with a sample size of 60 subjects. In the crossover paired comparison, the power also is greater than 99%.
- In order to detect the occurrence of side effects with at least a 5% frequency, the sample size was selected. With the proposed study design a total of 60 subjects will have safety data. With 45 subjects the probability of observing an event rate of 5% is 0.95 for the 60 subjects total, 0.90 for 45 subjects (treated vs control arm) and is 0.52 for the 15 subjects in the crossover arm. The probability of observing an event rate of 0.01 is 45% with 60 subjects.
- The additional 8 subjects above 72 is requested in order to accommodate treatment of subjects who have undergone the extensive screening and baseline evaluations from confirmation of eligibility to scheduling treatment within the center based upon availability of MR time.

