10.5 Safety

All safety analyses will be performed on the Safety and Crossover analysis populations – separately and combined, and will be descriptive and narrative in nature. Note that mock tables are presented for Safety population only. For Crossover and combined (Safety and Crossover) populations the tables will be prepared in the similar manner, presenting ExAblate group only. The following will be provided by treatment group:

- Adverse Events:
 - Descriptive statistics of Number of Adverse Events per Subject
(Error! Reference source not found.)
 - Frequency distribution of Experience of at Least One Adverse Event
(Error! Reference source not found.)
 - All Adverse Events (AEs) will be tabulated using Frequency tables with – Number of Incidents, Number of Subjects and Percentage of Subjects by:
 - Body System, Preferred Term and Resolution Time (within 30 days, within 31-90 days, more than 90 days), separately for Adverse Events started within 30 days post treatment, 31-90 days post treatment and more than 90 days post treatment
(Error! Reference source not found., Error! Reference source not found., Error! Reference source not found.).
Note that in case resolution date is missing, AE will be assigned to “Unresolved” category.
 - Body System, Preferred Term and Severity **(Error! Reference source not found.)**
 - Body System, Preferred Term and Relation to Treatment **(Error! Reference source not found.)**
 - Serious Adverse Events (SAEs):
 - Listing of all SAEs **(Error! Reference source not found.)**
 - In case the number of SAEs is greater than 12, all AE tables will be repeated, presenting SAEs only

- The Kaplan-Meier curve of AE's free percentage of subjects by time will be presented by treatment group. The groups will be compared using a Log-Rank test.

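### The only between-arm safety test, a log-rank on first AE of any kind, responds mainly to minor procedure-day symptoms and not to the treatment-related complications named in the protocol's safety endpoint

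*SAP*

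**What the plan says.** Protocol 2.1.1 bases primary safety on an "evaluation of the incidence and severity of device / treatment related complications". Section 2 adds that relative safety will be judged on a shared description of significant clinical complications.

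SAP 10.5 states that all safety analyses "will be descriptive and narrative in nature". It plans AE frequency tables by treatment group, including one by "Body System, Preferred Term and Resolution Time (within 30 days, within 31-90 days, more than 90 days"), produced separately by onset window, with events lacking a resolution date counted as unresolved. Further tables cover severity and relation to treatment, and all SAEs are listed. One inferential comparison follows: "The Kaplan-Meier curve of AE's free percentage of subjects by time will be presented by treatment group. The groups will be compared using a Log-Rank". The event is not restricted in any way, and no alpha, time horizon or censoring rule is given. The hierarchy in SAP 10.6.1 covers efficacy only.

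**The concern.** A subject leaves the AE-free curve at the first AE. If that is a headache on the treatment day, a deficit that appears later, or that appears the same day and lasts, adds nothing to the statistic. Protocol 6.2 itself separates side effects that normally clear within 1 to 14 days from significant ones with no defined time to resolution. The test pools the two, and the former are far more frequent.

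The p-value can therefore mislead both ways. It can be non-significant despite a large excess of lasting deficits, or significant because Sham subjects report fewer minor symptoms. SAP section 2 says the Main stage will be used to test device safety for regulatory approval. This is the only comparative safety p-value specified, and no estimate or interval for a between-arm difference in lasting harm is planned beside it.

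**Working it through.** **1. The plan's own safety figures.** Protocol 5.4 gives the chance of seeing at least one event, 1 − (1 − p)^n:

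- p = 5%, n = 60: 1 − 0.95^60 = 0.954 (stated 0.95)
- p = 5%, n = 45: 1 − 0.95^45 = 0.901 (stated 0.90)
- p = 5%, n = 15: 1 − 0.95^15 = 0.537 (stated 0.52)
- p = 1%, n = 60: 1 − 0.99^60 = 0.453 (stated 0.45)

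All agree within 2 points. They concern detection of a single event; no power is stated for the log-rank.

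**2. How common are treatment-day AEs?** Pilot data are in Protocol 1.4.2.1.2.4 (Table 2): 15 subjects and 82 events, or 82/15 = 5.5 per subject. The text says "Most of these events resolved either the same day (49% of the total events) or within 2 weeks of treatment". The share of subjects with at least one treatment-day AE is not reported.

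- Floor: one-day headache in 9 of 15 = 60%. This takes the table to count patients, as its introduction says, although the column header reads as events, and takes the headaches to start on the treatment day.
- If one-day headache (9), light-headedness (8), nausea (6), warm sensation (4) and emesis (2) were independent: 1 − (6 × 7 × 9 × 11 × 13)/15^5 = 0.93.
- If same-day events were Poisson with mean 0.49 × 82/15 = 2.7: 1 − e^(−2.7) = 0.93.

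**3. Why lasting harm is masked.** Let p be the day-0 transient AE rate in both arms, and hE and hS the persistent-deficit rates, independent of p. With deficits starting on day 0, the proportion failing is 1 − (1 − p)(1 − h), so the gap between arms is (1 − p)(hE − hS). A true gap of 40% − 3% = 37 points is multiplied by 1 − p.

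**4. Simulation.** Arm sizes are 56 and 20, as in the results table of the appended long-term follow-up protocol (section 18), and within "a total of a minimum of 72 and a maximum of 80 randomized subjects in a 3:1 (treated:sham control) ratio", that is 54:18 to 60:20. Assumed, not from the documents: all day-0, Sham and deficit rates, 30% background AEs over follow-up, truncation at day 90 and two-sided alpha 0.05.

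| Day-0 AE rate, both arms | Gap left on day 0 | Rejects, deficit 3% v 3% | Rejects, deficit 40% v 3% |
|---|---|---|---|
| 95% | 0.05 × 37 = 1.9 points | 4% | 5% |
| 80% | 0.20 × 37 = 7.4 points | 6% | 11% |
| 60% | 0.40 × 37 = 14.8 points | 5% | 17% |

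Other seeds and deficit onset times shift these by up to about 3 points. A log-rank on the persistent events alone rejects about 96-97% at 40% v 3%, but only about 41-46% at 20% v 3%.

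**5. Unequal day-0 rates, no excess lasting harm (3% in each arm).**

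- 95% v 70%: gap 0.97 × 25 = 24.3 points; the test rejects about 73%.
- 95% v 50%: gap 0.97 × 45 = 43.7 points; the test rejects about 98%.

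**6. Second set of assumptions.** At 54:18 with no background AEs, raising persistent harm from 5% v 5% to 30% v 5% moves rejection from 3% to 4% (day-0 rate 95%) and from 5% to 13% (day-0 rate 60%). A direct Fisher comparison of persistent events has about 57% power. At 45% v 5% with a 60% day-0 rate the log-rank reaches 28%, against about 95% directly. Sensitivity is heavily reduced there, but not lost.

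**The case against.** The strongest reply is that nothing hangs on this test. SAP 10.5 declares safety descriptive and gives no safety hypothesis, alpha or success rule. Lasting events will be visible by arm in the resolution-time tables, with severity, relatedness and SAEs shown as well. The DSMB reviews all AEs. This stands, and it limits the consequence: a reader might infer that the plan would hide lasting harm or that a safety claim depends on this p-value, and the documents support neither.

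A reader might also infer from 82 events in 15 subjects that nearly every treated subject fails on day 0. The documents support only the 60% floor; the higher figure needs independence or Poisson assumptions. The attenuation remains at 60%, so the point does not depend on it.

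Equal day-0 rates are likewise an assumption. Sham energy is disabled (Protocol 4.1.3) and Sham table time is nominally limited to 1 h 30 min, although the physician may match sonication time to the active arm (4.2.1.2). Exclusion criterion 14 allows for up to 4 hours on the table. A lower Sham rate is plausible, and rejection would then correctly show more AEs on ExAblate. That is a valid result for an any-AE test, but it still says nothing about lasting or significant complications.

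Finally, moving the log-rank to persistent neurological AEs is a tempting remedy that does not work well. Power is below one half at 20% v 3%. An event defined by later non-resolution also cannot be classified for late-onset Sham events once those subjects cross over after Month 3.

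**Conclusion.** The point holds as a mismatch between the one comparative safety test and the safety endpoint it sits beside. With equal day-0 AE rates of 60% to 95%, a 37-point excess of persistent deficit lifts rejection only from about 4-6% to about 5-17%. With fewer day-0 AEs on Sham (95% v 70% or 50%), the test rejects about 73-98% with no such excess. These sizes rest on assumed day-0, Sham and deficit rates, a day-90 horizon and alpha 0.05. The direction follows from counting only the first AE of any kind. The result is a p-value that should carry no weight in a safety statement, in a plan that offers no interval for the quantity that should. It does not invalidate the safety tables or any confirmatory conclusion.

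**What to change.** In SAP 10.5:

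- Keep the any-AE Kaplan-Meier curve as descriptive, state its time horizon and censoring rule, and state that its log-rank p-value supports no safety conclusion.
- Add the between-arm difference in the proportion of subjects with at least one device- or procedure-related AE unresolved at the Month 3 visit, before any crossover. Give it overall and for the nervous-system body class, with an exact 95% CI by a named method.
- Show the same estimate regardless of attribution, because relatedness is judged by investigators and the treating physician knows the assignment (Protocol 4.1.1).
- Base the safety statement on the estimate and its upper limit, not on a test.

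The relation, body-system and resolution fields are already collected and tabulated, so the cost is SAP wording and one table. The drawback is few events and a wide interval: even 0 of 56 gives a one-sided 95% upper bound of 1 − 0.05^(1/56) = 5.2%, and 20 Sham subjects widen the interval for the difference further. The body-class result also depends on AE coding supplied by the sponsor (SAP section 8).

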10.6 Efficacy

10.6.1 Adjustment for Multiple Comparisons

This study has one primary and three secondary efficacy confirmatory endpoints. In order to control for multiplicity across the confirmatory endpoints, we will employ a hierarchical testing design. The primary efficacy analysis will be performed with a significance level of alpha = 0.05. Dependent on the successful confirmatory testing of the primary efficacy analysis, we will proceed with testing each of the three secondary efficacy confirmatory endpoints in the order listed in Section 6.2.2, proceeding with each test with alpha = 0.05 if all previous tests were successful. No confirmatory statements will be made about endpoints that are listed lower on the hierarchy after an endpoint fails testing. This way we will control the Type 1 error across all endpoints tested in this study.

10.6.2 Confirmatory Primary Efficacy

Primary efficacy analyses will be conducted on the ITT analysis population and will test the following hypothesis:

$$H_0: M3_{\text{ExAblate}} \leq M3_{\text{Sham}}$$

$$H_1: M3_{\text{ExAblate}} > M3_{\text{Sham}}$$

Where, $M3_{\text{ExAblate}}$ and $M3_{\text{Sham}}$ are means of Primary Endpoint (PE), as defined in Section 6.2.1, in the ExAblate and Sham groups, respectively.

This hypothesis will be analyzed using independent groups t-test with two-sided alpha=0.05, should the data not differ appreciably from normal theory. Otherwise, the Wilcoxon rank-sum test will be applied.

We will have succeeded if the Null is rejected and mean PE is higher in ExAblate than Sham. Descriptive statistics of the primary endpoint and comparison p-value will be provided (**Error! Reference source not found.**).

10.6.3 Confirmatory Secondary Efficacy

As indicated in Section 6.2.2, this study has three confirmatory secondary endpoints (SE1, SE2 and SE3). Hierarchical testing design will be applied to control for multiple statistical testing (as explained in Section 10.6.1).

SE1 Analysis:

The first confirmatory secondary efficacy analysis will be conducted on the ITT analysis population. The following hypothesis will be tested for SE1:

$$H_0: Q3_{\text{ExAblate}} \leq Q3_{\text{Sham}}$$

$$H_1: Q3_{\text{ExAblate}} > Q3_{\text{Sham}}$$

Where, $Q3_{\text{ExAblate}}$ and $Q3_{\text{Sham}}$ are means of the first Secondary Endpoint (SE1), as defined in Section 6.2.2, in the ExAblate and Sham groups, respectively.

This hypothesis will be analyzed using independent groups t-test with two-sided alpha=0.05, should the data not differ appreciably from normal theory. Otherwise, the Wilcoxon rank-sum test will be applied. Descriptive statistics and comparison p-value will be provided (**Error! Reference source not found.**).

SE2 Analysis:

The second confirmatory secondary efficacy analysis will be conducted on the ITT (subjects from ExAblate group only) population. The following hypothesis will be tested for SE2:

$$H_0: M12_{\text{ExAblate}} \leq 0$$

$$H_1: M12_{\text{ExAblate}} > 0$$

Where, $M12_{\text{ExAblate}}$ is the mean of the second Secondary Endpoint (SE2), as defined in Section 6.2.2, in the ExAblate group.

This hypothesis will be analyzed using one-sample t-test with two-sided Alpha = 0.05, should the data not differ appreciably from normal theory. Otherwise, the one-sample Wilcoxon signed rank test will be applied. Descriptive statistics and comparison p-value will be provided (**Error! Reference source not found.**).

SE3 Analysis:

The third confirmatory secondary efficacy analysis will be conducted on the ITT analysis population. The following hypothesis will be tested for SE3:

$$H_0: C3_{\text{ExAblate}} \leq C3_{\text{Sham}}$$

$$H_1: C3_{\text{ExAblate}} > C3_{\text{Sham}}$$

Where, $C3_{\text{ExAblate}}$ and $C3_{\text{Sham}}$ are means of the third Secondary Endpoint (SE3), as defined in Section 6.2.2, in the ExAblate and Sham groups, respectively.

This hypothesis will be analyzed using independent groups t-test with two-sided alpha=0.05, should the data not differ appreciably from normal theory. Otherwise, the Wilcoxon rank-sum test will be applied. Descriptive statistics and comparison p-value will be provided (**Error! Reference source not found.**).

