2.2 Secondary Endpoints

The secondary endpoints of the study are as follows:

1. Quality life claims: Questionnaire for Essential Tremor (QUEST) outcome (upper extremity questions) at Months 3 change from Baseline as compared between treatment groups

2. Durability (as measured by QUEST upper arm extremity questions) of the procedure as reflected by the efficacy data through change from baseline measures through Month 12 follow up
3. Subject daily functionalities: as measured by CRST Part-C (subscores) Month 12 as compared to Baseline, and between treatment groups through Month 3.
4. Crossover cohort treatment outcome (perform 1-3 as above for the Crossover cohort)

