6.2.2 Confirmatory Secondary Endpoints

The confirmatory secondary efficacy endpoints in this study are the following:

- SE1=Improvement from Baseline at three months in Quality of Life in Essential Tremor (QUEST). SE1 will be calculated as follows:
 - Categorize the 30 questions into 5 dimensions as follows:
 - Communication: #1 – #3
 - Work and Finances: #4 – #9
 - Hobbies and Leisure: #10 – #12
 - Physical: #13 – #21
 - Psychosocial: #22 – #30
 - Score all applicable questionnaire answers as follows:
 - Never = 0
 - Rarely = 1
 - Sometimes = 2
 - Frequently = 3
 - Always = 4

Note:

- ✓ All questions answered “N/A” will be excluded from the calculation (only questions 4, 5, 7, 8 and 14 can be answered “N/A”)

- ✓ Questions 6, 7, 11 and 12 can only be scored at two values – either a 0 or a 4
- For each subject, calculate dimension score as a percentage of total possible score for each dimension separately. Denote dimension score for dimension [i] at visit [k] as $DS_{[i,k]}$, then:

$$DS_{[i,k]} = \frac{\text{Total applicable points}_{[i,k]}}{\text{Total possible points} (\# \text{ of applicable questions} \times 4)_{[i,k]}} \times 100$$

Note: missing data should be imputed as described in Section 7.2.1.

- For each subject, calculate QUEST summary of dimensions total score as a mean of the five dimension scores. Denote QUEST summary of dimensions total score at visit [k] as $QUEST_{[k]}$, then:

$$QUEST_{[k]} = \frac{\sum_{i=1}^5 DS_{[i,k]}}{5}$$

Note: lower QUEST_[k] scores are better than higher scores.

- For each subject, calculate SE1 as follows:

$$SE1 = \frac{QUEST_{[\text{Baseline}]} - QUEST_{[3 \text{ months FU}]}}{QUEST_{[\text{Baseline}]}}$$

Note: higher SE1 values represent improvement.

- SE2=Percent Improvement from Baseline at twelve months post-treatment in the treated (contralateral) upper extremity CRST sub score. SE2 will be calculated similarly to PE from the previous section, based on 12 months FU data.
- SE3=Percent Improvement from Baseline at three months post-treatment in functional disabilities CRST total score, as measured by CRST Part C. Note, that Part C is performed by Site Assessor only. SE3 will be calculated for each subject as follows:
 - Denote functional disabilities CRST Part C total score at visit [k] as $CRST_C_{[k]}$, then:

CRST_C_[k] = average of answers to items #16-#23 at visit [k]

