10.2 Baseline Characteristics

Baseline characteristics will be analyzed using the Safety analysis population.

Descriptive statistics or frequency distribution, as appropriate, by treatment group will be provided for the following:

- Demographic Characteristics and Vital Signs:
 - Age, BMI, Height, Weight (**Error! Reference source not found.**)
 - Gender, Race (**Error! Reference source not found.**)
- Medical History:
 - Significant medical conditions (other than the present disease) (**Error! Reference source not found.**)
 - Other significant medical conditions (protocol specific) (**Error! Reference source not found.**)
- Essential Tremors History:
 - Time from Initial ET Symptoms (**Error! Reference source not found.**)
 - Time from Initial ET Diagnosis (**Error! Reference source not found.**)
 - Time from First ET Medical Therapy (**Error! Reference source not found.**)
 - Family History of ET (**Error! Reference source not found.**)
 - Listing of subjects having family history of ET along with specification of relationship degree and the number of relatives (**Error! Reference source not found.**)
 - Indication of etiology due to neuroleptic drug exposure (**Error! Reference source not found.**)
 - Is subject considered medication refractory? (**Error! Reference source not found.**)
- MRI Examination (**Error! Reference source not found.**):
 - Any arteriovenous malformations that require treatment
 - Any aneurysms that require treatment
 - Evidence of a recent hemorrhage
- CT Examination (**Error! Reference source not found.**):
 - Any calcifications present within the treated area
 - Any implants within the skull or brain
 - Is the skull suitable for treatment?
 - History of DVT or systemic thrombosis

- Evidence of acute thrombosis in lower extremities for subjects who had a history of DVT or systemic thrombosis
- CRST and QUEST questionnaire parameters at Baseline, as defined in Sections 6.2.1 and 6.2.2 (**Error! Reference source not found.**):
 - The Treated (Contralateral) Upper Extremity CRST Sub Score (CRST_[contralateral, Baseline])
 - QUEST Summary of Dimensions Total Score (QUEST_[Baseline])
 - Functional Disabilities CRST Part C Total Score (CRST_C_[Baseline])

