10.6.4 Additional Secondary Efficacy

Additional secondary efficacy analyses will repeat those in the preceding sections (confirmatory primary and secondary efficacy analyses), when using PP analysis population instead of ITT (**Error! Reference source not found.**, **Error! Reference source not found.**).

Analysis of additional secondary efficacy endpoints (defined in Section 6.2.3) will be conducted on both ITT and PP analysis populations.

Descriptive statistics of raw values and change or percent change from baseline, as appropriate, over time by treatment group will be provided for the following:

- Clinical Rating Scale for Tremor (CRST) Parameters:
 - Part A and B CRST, separately for treated and non-treated side of the body (**Error! Reference source not found.**, **Error! Reference source not found.**)
 - Part B Score for treated side of the body, for each motor task (**Error! Reference source not found.** – **Error! Reference source not found.**)
 - Part C Score for each item and Overall (**Error! Reference source not found.** – **Error! Reference source not found.**)
 - Overall CRST Score (**Error! Reference source not found.**)
- Quality of Life in Essential Tremor Questionnaire (QUEST) Parameters:
 - Overall Quality of Life Score (**Error! Reference source not found.**)

- Waking Hours with Tremor in Any Body Part (**Error! Reference source not found.**)
- Tremor Severity Score, separately for each category (**Error! Reference source not found. – Error! Reference source not found.**)
- QUEST Parameters (based on questions 1-30):
 - Dimension Score, separately for each dimension (**Error! Reference source not found. – Error! Reference source not found.**)
 - Summary of Dimensions Total Score (**Error! Reference source not found.**)

In addition, where appropriate, the following will be provided:

- Graphical presentation over time by treatment group
- Statistical testing to compare:
 - between treatment groups, by visit
 - within each treatment group, comparing Baseline to each follow-up visit
 - between treated and non-treated sides, within each treatment group, by visit

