10.6.5 Covariate Analyses

The effects of covariates will be assessed for all confirmatory primary and secondary efficacy analyses.

The following covariates will be examined:

- Age
- Baseline CRST Score (CRST_[contralateral, Baseline])
- Gender
- Center

Center is expected to have several categories. Keeping the number of categories as is will, in some cases, yield small subgroups and substantially reduce power. To address this issue, categories will be combined by grouping those with few observations into a

single category. Grouping of categories will be specified after category frequency have been produced but before statistical testing.

The following will be provided:

1. Analyses for PE, SE1 and SE3 will be conducted on ITT analysis population comparing ExAblate and Sham groups. The following model will be applied:

$$Y = \text{Covariate} + \text{Treatment Group} + \text{Covariate} * \text{Treatment Group}$$

Where,

Y = PE, SE1 or SE3, depending on the analysis

Covariate = covariate of interest

*Covariate*Treatment Group* = covariate by group interaction

Models both with and without *Covariate*Treatment Group* interaction will be considered (**Error! Reference source not found.**).

Statistical testing will be done by linear regression. In case the distribution of Y is extremely not normal, the non-parametric methods will be applied depending on the emerged distribution.

Descriptive statistics of each endpoint will be presented by covariate levels and treatment group. For this purpose numerical covariates (Age and Baseline CRST Score) will be categorized into equal subgroups inside the emerged range of values (**Error! Reference source not found.**, **Error! Reference source not found.**, **Error! Reference source not found.**).

Assessing the effect of a covariate on treatment will be done by examining the degree to which the significance of the Treatment Effect changes with the inclusion of the covariate (**Error! Reference source not found.**). Weakening or strengthening of the Treatment Effect in the presence of a covariate will be interpreted using both clinical and statistical considerations.

2. Analyses for SE2 will be conducted on the ITT (subjects from ExAblate group only) population and will repeat the second confirmatory secondary efficacy analysis for each level of covariate separately. For this purpose numeric covariates (Age and Baseline CRST Score) will be categorized into equal subgroups inside the emerged range of values.

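### SE1 (QUEST at Month 3) is tested without its own baseline: adding baseline QUEST to the model is a low-cost efficiency gain, not the correction of an error

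*SAP*

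**What the plan says.** SAP 6.2.2 defines SE1 for each subject as (baseline QUEST - Month 3 QUEST) / baseline QUEST, where QUEST is the mean of five dimension scores. SAP 10.6.3 compares the arms on that ratio: "This hypothesis will be analyzed using independent groups t-test with two-sided alpha=0.05, should the data not differ appreciably from normal theory". If the data look non-normal, a rank-sum (Wilcoxon) comparison replaces it. Neither test has a covariate.

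SAP 10.6.1 places SE1 directly after the primary endpoint (PE) and adds: "No confirmatory statements will be made about endpoints that are listed lower on the hierarchy after an endpoint fails testing". SE2 and SE3 therefore depend on SE1.

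QUEST is collected at screening and at baseline (Protocol 4.3, SAP 4), and its baseline score is tabulated by arm (SAP 10.2). SAP 10.6.5 fits supportive regressions for PE, SE1 and SE3, one covariate at a time: age, contralateral baseline CRST, gender and center. Baseline QUEST is not listed there or among the confounders in Protocol 5.6. SAP 10.6.4 offers "Descriptive statistics of raw values and change or percent change from baseline, as appropriate, over time by treatment group", with between-arm tests by visit, and names no covariate. Protocol 2.2 words the endpoint as the QUEST "outcome (upper extremity questions) at Months 3 change from Baseline as compared between treatment groups".

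**The concern.** An endpoint's own baseline is often a strong predictor of its follow-up value. Here SE1 can be adjusted for another scale's baseline but not for its own, although the score is in hand. PE does have its own baseline on the 10.6.5 list.

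The ratio also has a baseline score in its denominator, and entry sets no minimum QUEST. A given change in points counts for more in a subject with a low baseline, which can add noise.

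What is at stake is power at the first step of the hierarchy. If SE1 misses, SE2 and SE3 lose confirmatory status however strong they are. The protocol's only power statement concerns CRST.

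**Working it through.** **1. The plan's own power figure.** Protocol 5.4 states that "the power to detect a change in the treated vs sham control is greater than 99% with a sample size of 60 subjects". It gives a baseline of 20.4 and drops of 78% and 4%, but no SD. The difference is 20.4 x (0.78 - 0.04) = 15.1 points. At 45:15 and two-sided 0.05, 99% power needs SD <= 15.1 / [(1.960 + 2.326) x sqrt(1/15 + 1/45)] = 11.8 points (SD 10: 99.9%; SD 12: 98.8%). The figure is plausible. It says nothing about QUEST.

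**2. Where SE1 stands among the between-arm tests.** This uses results reported later, in section 18 of the follow-up protocol (ET002-LTF), so it is context only. SD = half-width / t(0.975, n-1) x sqrt(n).
- QUEST: 11.0 / 2.004 x sqrt(56) = 41.1 and 25.55 / 2.101 x sqrt(19) = 53.0; pooled 44.3. Standardised difference (43.2 - 5.0) / 44.3 = 0.86.
- PE: SDs 24.6 and 20.4; pooled 23.6; 47.0 / 23.6 = 1.99.
- Part C (SE3): SDs 31.9 and 19.0; pooled 29.1; 62.0 / 29.1 = 2.13.

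t-test power for SE1 is then about 0.88 at 54:18 and 0.81 at 45:15 (Welch 0.76 and 0.68). PE and SE3 exceed 0.999, so no gain is claimed there. These SDs are rough. The QUEST intervals are lopsided around their estimates (-8.9/+13.1 and -19.9/+31.2), how they were formed is not stated, and a pooled t-test on these SDs gives p of about 0.002, not the reported p<0.001.

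**3. The denominator.** One step on one of the three Communication items moves QUEST by (1/12 x 100)/5 = 1.67 points. That is 16.7% of a baseline of 10 and 3.3% of a baseline of 50.

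**4. Simulation.** From the documents: 3:1 allocation, 72 subjects (54:18), two-sided 0.05. Assumed, because the documents are silent: gamma baseline with mean 40, SD 12-20, correlation 0.5-0.7, improvement 25% vs 5%. Models A-C have regression to the mean (A: gamma copula, proportional effect; B: linear with normal residual, proportional; C: linear, additive; 27 scenarios). In D and E, error scales with baseline (normal on the percent scale; lognormal; 12 scenarios). There were 8000 replicates per scenario. Power at SD 16, with correlation 0.6 (A-C) or error 0.4 (D-E):

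| Model | t-test, percent | Wilcoxon, percent | Percent + baseline QUEST | Score ANCOVA | Score ANCOVA, HC3 |
|---|---|---|---|---|---|
| A | .632 | .613 | .717 | .774 | .693 |
| B | .535 | .551 | .608 | .777 | .679 |
| C | .509 | .527 | .528 | .617 | .589 |
| D | .456 | - | .453 | .412 | .389 |
| E | .572 | - | .565 | .528 | .425 |

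Ranges over all scenarios, in percentage points of power:
- Percent + baseline QUEST (model-based SE) against the t-test: 0 to +10 in A-C, and a loss of less than 1 in D-E. Against Wilcoxon: -3 to +11 in A-C, +2 to +3 in D-E.
- Score ANCOVA against the t-test: +3 to +29 in A-C (HC3 +1 to +18), but -3 to -9 in D-E (HC3 -6 to -16).

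A separate run at 45:15 (correlation 0.4-0.8, 25% over sham, regression to the mean only) put percent + baseline at about -1 to +14 against the t-test. Its worst result against Wilcoxon was .751 vs .796, or -4.5.

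**5. Type I error.** Null rejection was 0.043-0.056 for all five tests at 54:18. At 45:15 it was 4.2-5.2% for the t-test and 4.7-5.6% for score ANCOVA.

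**6. At the reported effect (43.2% vs 5.0%).** In the mid case the t-test already has .998/.985/.973 (A/B/C), so no test can add more than 1 - .973 = 2.7 points; HC3 score ANCOVA adds 0-1. In the scenario closest to the reported SDs (C, SD 20, correlation 0.7) the t-test has .922, Wilcoxon .945 and HC3 score ANCOVA .955: gains of 3 and 1.

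**The case against.** The strongest reply is that nothing here is wrong. Percent improvement is used consistently for PE, SE1 and SE3, and Protocol 5.4 itself reasons in percent drops. The follow-up protocol (15.7) records FDA approval of the SAP. SE1 already has supportive covariate models, and the Wilcoxon fallback deals with a skewed ratio. Very low baselines should be uncommon, because inclusion criterion 10 requires a CRST disability item of 2 or more. In the simulated baselines only 0.01%, 0.4% and 1.9% (SD 12, 16, 20) fall below 10. All of this stands, and it makes Wilcoxon a fair comparator. None of it supplies an analysis of SE1 adjusted for baseline QUEST.

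The second reply is that the sign of the gain depends on an error structure that the documents do not describe. That also stands, and it bears most heavily on score ANCOVA. A reader might infer from rows A-C that score ANCOVA is simply the better test. Rows D and E contradict this. A further simulation, with additive test-retest noise plus variable proportional response, put HC3 score ANCOVA at about -7 to +3 points against Wilcoxon.

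A reader might also propose to let screening and baseline QUEST pairs decide the scale. That assumes screening-to-baseline error has the same form as baseline-to-Month 3 error, which nothing in the documents supports. Subjects are also unblinded individually at Month 3 (Protocol 4.1.1), so some would probably be unblinded before the last pairs were available.

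**Conclusion.** The point holds as an efficiency improvement for SE1 only. The planned test ignores a baseline that the trial collects, at the first step after PE. Under the assumed QUEST values, the lowest-risk adjustment changes power by about -1 to +10 points against the t-test and can trail Wilcoxon by about 3. Score ANCOVA offers up to about 18 points with HC3 (29 model-based) under regression to the mean, at the price of a loss of 3-9 (HC3 6-16) if error scales with baseline. Each figure rests on an assumed mean, SD, correlation and effect. At the reported effect the gain is small, about 0-3 points in the two cases examined.

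Two stronger readings are not supported. One is that the SE1 test is invalid: randomisation protects it, and simulated Type I error stays near 5%. The other is that the trial's conclusions are in doubt: SE1 was reported at p<0.001, so the hierarchy was not blocked there.

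**What to change.** Before data review, pre-specify one baseline-adjusted test for SE1, with the scale fixed in advance and no choice made from trial data.

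- Lowest-risk version: keep percent improvement as the endpoint and test it in a linear model with treatment and baseline QUEST. State the SE method, which matters at 3:1. Keep Wilcoxon on percent improvement as a sensitivity analysis.
- Name an ANCOVA of Month 3 QUEST on treatment and baseline QUEST as a supportive analysis. Make it the main test only if the sponsor accepts a result in points and the possible power loss.
- In SAP 10.6.5, add baseline QUEST to the covariates for SE1.

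The cost is a SAP amendment, agreed with FDA as Protocol 5.8 provides, and some programming; no new data are needed. Since results are already reported, for this trial the analysis can only be a labelled sensitivity analysis. The change does not settle whether SE1 uses the upper extremity questions (Protocol 2.2) or all 30 items (SAP 6.2.2), which must be reconciled separately.
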